### 8.6.1.1 Multiplicity

Multiplicity adjustment will be made for primary analysis in this study.

Strongest control of type I error at 0.05 will include an equal Bonferroni split alpha (0.025) for each of the primary endpoints. Multiple active dose groups will be compared to placebo (high dose versus placebo, low dose versus placebo). The high dose group for each will be analyzed first for each endpoint. If statistical significance at the 0.025 level is achieved the low dose group will be tested. If statistical significance is not achieved for the high dose, the low dose group will not be tested.

The Flow Chart of Testing Strategy is presented in [Figure 2](#). This flow chart is for each of the two primary endpoints.

**Figure 2: Flow Chart of Testing Strategy**

### 8.6.1.2 Treatment by center interaction analysis (multi-center study)

No analysis will be made to assess the treatment-by-center interaction.

### 8.6.2 Analysis of primary efficacy endpoint(s)

The primary efficacy analysis is a set of two primary endpoints. The primary endpoints comprise of proportion of subjects who achieve:

- $\geq 1$  stage improvement in liver fibrosis without worsening of steatohepatitis
- Resolution of steatohepatitis without worsening of liver fibrosis

as determined by liver biopsy at week 72. Derivation for steatohepatitis and fibrosis conditions (like improvement, worsening and resolution) are provided in [Table 2](#).

A responder will be defined for each primary endpoint separately. Any subject achieving the primary endpoint will be a responder for that primary endpoint. Subjects will not be categorized as responder or non-responder in case of missing response (score).

The objective related to the primary endpoint is to evaluate the effect of EDP-305 compared to placebo with respect to proportion of responders defined as above.

The hypothesis to test EDP-305 2 mg and placebo is formulated as:

- $H_{01}: OR = 1$  v/s  $H_{11}: OR \neq 1$

Where OR is the odds ratio at week 72 for EDP-305 2mg and placebo treatment groups respectively.

The hypothesis to test EDP-305 1.5 mg and placebo is formulated as:

- $H_{02}: OR = 1$  v/s  $H_{12}: OR \neq 1$

Where OR is the odds ratio at week 72 for EDP-305 1.5mg and placebo treatment groups respectively.

The proportion of responders for each endpoint will be compared using a logistic regression model with treatment group, diabetes status and use of Vitamin E and/or pioglitazone as fixed effects and baseline NAS score as covariate. Treatment groups will be compared for each endpoint at a 0.025 significance level. The odds ratio, 97.5% confidence interval and the p-value will be presented. In the event that the logistic regression model is unable to converge, a Cochran-Mantel-Haenszel test will be performed using the stratification factors of diabetes status and Vitamin E/pioglitazone use status. The frequency counts for responders and non-responders will also be presented in the table. The primary efficacy analyses will be performed using the ITT population. As an additional analysis, the primary endpoint will also be analyzed using PP population. Multiplicity control for this testing is noted in [Section 8.6.1.1](#).

A by-subject listing will be provided for the primary efficacy endpoints.

### 8.6.2.1 Sensitivity Analysis

As a sensitivity analysis, the methodology utilized for the primary endpoints will be performed on all ITT subjects where those missing primary endpoint data will be imputed as a non-responder.

### 8.6.3 Analysis of secondary efficacy endpoint(s)

All analysis of secondary efficacy endpoints will be performed on the ITT population. Secondary endpoint related to PK data will be analyzed using subjects in the PK population. Secondary endpoints will be analyzed for treatment group differences.

#### 8.6.3.1 Categorical Endpoints (Responder at Week 72)

Secondary endpoints with categorical values are defined as below:

Proportion of subjects with

- improvement of fibrosis by at least 1 stage and/or resolution of NASH without worsening of either as determined by liver biopsy at week 72
- no worsening of fibrosis combined with no worsening of NASH as determined by liver biopsy at week 72
- resolution of fibrosis as determined by liver biopsy at week 72
- improvement in each histologic feature of NASH, by at least 1 point as determined by liver biopsy at week 72
- improvement of fibrosis by  $\geq 2$  stages by liver biopsy at week 72
- improvement in NAS by at least 2 points with no worsening of fibrosis as determined by liver biopsy at week 72
- improvement of fibrosis and resolution of NASH as a composite endpoint as defined by both endpoints being met in the same subject
- resolution of NASH and no worsening of liver fibrosis
- histological progression to cirrhosis as determined by liver biopsy at week 72

Any subject who satisfies the criteria for the secondary endpoint will be a responder for that endpoint.

The proportion of responders for each endpoint will be compared using a logistic regression model with treatment group, diabetes status and use of Vitamin E and/or pioglitazone as fixed effects and baseline NAS score as covariate at week 72. Treatment groups will be compared for each endpoint at a 0.05 significance level. Odds ratio, 95% confidence interval and p value will be reported in the table.

A Cochran-Mantel-Haenszel test stratifying by diabetes status and Vitamin E/pioglitazone usage will be utilized to test the treatment group differences in case of lack of convergence. The frequency counts for responders and non-responders along with the p-value will be presented in the table.

A by-subject listing will be provided for observed and derived variables.

### **8.6.3.2 Continuous Endpoints**

Secondary endpoints with continuous values are defined as below:

#### **8.6.3.2.1 Change from baseline in 5D-itch scale and Visual Analog Score (VAS) through week 72**

Pruritus will be monitored in this study at day 1, 7, weeks 2, 4, 8, 12, 16, 20, 24, 28, 32, 36, 40, 44, 48, 56, 64, 72 and EOS.

Observed values, change from baseline, and percentage change from baseline for VAS scores and each dimension of 5D-itch scale and overall score will be summarized using an 8-number summary by visit and treatment group.

Change from baseline for VAS and 5D-itch scale will be analyzed using a restricted maximum likelihood-based mixed model repeated measures (MMRM) technique. The model will include treatment, visit, treatment-by-visit interaction as fixed effects along with baseline NAS score and baseline score for VAS and 5D-itch scale as covariate respectively. Variance-covariance structure to be used to model the within-patient error and results to be presented are described in [Section 8.6.1](#). The details for calculation of score is given in [Appendix B](#).

A by-subject listing will be provided for observed and derived variables for VAS and 5D-itch scale.

#### **8.6.3.2.2 Change from baseline in percentage of fat in the liver as assessed by magnetic resonance imaging proton density fat fraction (MRI-PDFF) at week 12 and week 72**

Percentage of fat in the liver assessed by MRI-PDFF at screening, week 12 and week 72, change from baseline and percentage change from baseline will be summarized using an 8-number summary by visit and treatment group.

Change from baseline in percentage of fat in the liver at week 12 and week 72 will be analysed using an analysis of covariance (ANCOVA) model with treatment, baseline diabetes status and use of Vitamin E and/or pioglitazone as fixed effect along with baseline NAS score and baseline MRI-PDFF value as covariate. Least-squares means (using type III sum-of-squares), standard errors, p-value and 2-sided 95% confidence interval for treatment differences will be presented for week 12 and week 72. Significance tests will be based on least-squares means using a two-sided  $\alpha = 0.05$ .

A by-subject listing will be provided for observed and derived variables.

#### **8.6.3.2.3 Change from baseline in liver stiffness as assessed by magnetic resonance elastograph (MRE) at week 12 and week 72**

The liver stiffness assessed by MRE at screening, week 12 and week 72, change from baseline and percentage change from baseline will be summarized using an 8-number summary by visit and treatment group.

Change from baseline in liver stiffness at week 12 and week 72 will be analysed using an analysis of covariance (ANCOVA) model with treatment, baseline diabetes status and use

## Final Analysis Statistical Analysis Plan (SAP)

of Vitamin E and/or pioglitazone as fixed effect along with baseline NAS score and baseline MRE value as covariate. Least-squares means (using type III sum-of-squares), standard errors, p-value and 2-sided 95% confidence interval for treatment differences will be presented for week 12 and week 72. Significance tests will be based on least-squares means using a two-sided  $\alpha = 0.05$ .

A by-subject listing will be provided for observed and derived variables.

### 8.6.3.2.4 Change from baseline in TG, total cholesterol (TC), HDL cholesterol, LDL cholesterol and adiponectin through week 72

The parameters, TG, TC, HDL cholesterol, LDL cholesterol and adiponectin are captured in lipid profile panel. All these parameters will be monitored in this study at day 1, weeks 2, 4, 8, 12, 16, 20, 24, 28, 32, 36, 40, 44, 48, 56, 64, 72 and EOS.

Observed values, change from baseline, and percentage change from baseline for the parameters triglyceride (TG), total cholesterol (TC), HDL cholesterol, LDL cholesterol and adiponectin will be summarized using an 8-number summary by visit and treatment group.

Change from baseline for each of the above parameters will be analyzed separately using a restricted maximum likelihood-based mixed model repeated measures (MMRM) technique. The model will include treatment, visit, treatment-by-visit interaction as fixed effects along with baseline NAS score and baseline value of the respective parameters as covariate. Variance-covariance structure to be used to model the within-patient error and results to be presented are described in [Section 8.6.1](#).

A by-subject listing will be provided for observed and derived variables.

### 8.6.3.2.5 Pharmacokinetic concentrations of EDP-305 (and metabolites)

PK samples will be collected at day 1, weeks 2, 4, 8, 12, 16, 20, 24, 28, 32, 36, 40, 44, 48, 56, 64, and 72. On Day 1 and weeks 12, 36, and 72.

The detailed information related to pharmacokinetics analysis is provided in [Section 8.10](#).

[Redacted content]

**Final Analysis**  
**Statistical Analysis Plan (SAP)**

[Redacted text block containing multiple paragraphs of information, all obscured by black bars.]

A by-subject listing will be provided for Quality of Life Assessment.

[Redacted text block containing three lines of information, all obscured by black bars.]

# Final Analysis Statistical Analysis Plan (SAP)

## 8.7 Safety Analyses

All safety analyses will be based on the safety population and will be performed for all safety variables specified below.

No statistical tests will be performed.

### 8.7.1 Adverse events

All Adverse Events (AEs) will be classified by Primary System Organ Class (SOC) and Preferred Term (PT) according to the Medical Dictionary for Regulatory Activities (MedDRA) Version 23.0 or higher. All subjects in the safety analysis set will be included in the summaries.

AEs will be classified as pre-treatment AEs and treatment emergent adverse events (TEAEs) and are defined as follows:

**Pre-treatment AE:** A pre-treatment event is any event that meets the criteria for an AE/SAE and occurs after the subject signs the ICF but before receiving the first administration of study drug.

**TEAE:** A TEAE is defined as an AE occurring or worsening on or after the first dose of study drug until the last dose of study drug.

#### **Relationship of each AE to study drug:**

Related: There is an association between the event and the administration of study drug, a plausible mechanism for the event to be related to the study drug and causes other than the study drug have been ruled out, and/or the event re-appeared on re-exposure to the study drug.

Possibly Related: There is an association between the event and the administration of the study drug and there is a plausible mechanism for the event to be related to study drug, but there may also be alternative etiology, such as characteristics of the subject's clinical status or underlying disease.

Unlikely Related: The event is unlikely to be related to the study drug and likely to be related to factors other than study drug.

Not Related: The event is related to an etiology other than the study drug (the alternative etiology must be documented in the study subject's medical record).

## Final Analysis Statistical Analysis Plan (SAP)

### Grade AEs:

Grade AEs (serious and non-serious) in accordance with the NCI/CTCAE scale as presented below. Refer the [https://evs.nci.nih.gov/ftp1/CTCAE/CTCAE\\_4.03\\_2010-06-14\\_QuickReference\\_8.5x11.pdf](https://evs.nci.nih.gov/ftp1/CTCAE/CTCAE_4.03_2010-06-14_QuickReference_8.5x11.pdf) provided in reference for the same:

- **Mild** (Grade 1) asymptomatic or mild symptoms; clinical or diagnostic observations only; intervention not indicated
- **Moderate** (Grade 2) minimal, local or noninvasive intervention indicated; limiting age-appropriate instrumental activities of daily living
- **Severe** (Grade 3) Severe or medically significant but not immediately life threatening; hospitalization or prolongation of hospitalization indicated; disabling; limiting self-care activities of daily living
- **Life-threatening** (Grade 4) Life-threatening consequences; urgent intervention indicated
- **Death** (Grade 5) Death related to the AE.

Details for imputing missing or partial start dates of adverse events are described in [Section 7.2.2](#). Imputed Adverse Event dates will be used for determining treatment-emergence.

Summaries of AEs will include the following:

- TEAEs
- Related TEAEs
- Maximum Severity TEAEs
- TEAEs by severity
- TEAEs leading to study drug discontinuation
- TEAEs leading to study discontinuation
- AEs leading to death
- SAEs
- Related Treatment-Emergent SAEs

All TEAEs will be summarized by SOC, PT and treatment group using frequency counts and percentages. In addition, an overall summary for the categories above will be prepared by treatment group and overall.

On-treatment AEs will be summarized separately from those events that occurred during treatment-free follow-up. Those events that occurred during treatment-free follow-up will be summarized by randomized treatment group. The denominator for these events will be only those subjects who entered into the 4 week treatment free follow-up period.

Where a subject has the same adverse event, based on preferred terminology, reported multiple times in the treatment period, the subject will only be counted once at the preferred terminology level in adverse event frequency tables.

Where a subject has multiple adverse events within the same system organ class in the treatment period, the subject will only be counted once at the system organ class level in adverse event frequency tables.

When reporting adverse events by severity, in addition to providing a summary table based on the event selection criteria detailed above, summary table will also be provided based on the most severe event during the treatment period - independent of relationship to study treatment.

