Overall, EDP-305 was generally safe, with the majority of TEAEs being mild to moderate. The most common ( $\geq 5\%$ ) TEAEs with EDP-305 included pruritus, rash, gastro-intestinal (GI) related symptoms (nausea, vomiting, diarrhea), urinary tract infection, dizziness, decreased appetite and cough. As for tolerability of EDP-305 in this 12-week phase 2a study, pruritus was present in approximately 51% of the subjects in the 2.5 mg arm compared to less than 10% in the 1 mg arm and less than 5% in the placebo arm, with the majority being mild or moderate in severity. Among subjects with severe pruritus, there were 2 subjects in the 2.5 mg arm and 2 subjects in the 1 mg arm compared to none in the placebo arm. There were no study discontinuations due to severe pruritus except for one subject in the 1 mg arm. Overall, the incidence of treatment discontinuation due to pruritus was 1.8% for 1 mg and 20.8% for 2.5 mg and none in the placebo arm, with all the discontinuations in the 2.5 mg arm being due to moderate pruritus.

Based on Common Terminology Criteria for Adverse Events (CTCAE) grading, there were very few treatment-emergent laboratory abnormalities in the EDP-305 arms: Grade 3 increase in serum/plasma glucose were observed more frequently in subjects taking EDP-305 with 7% in the 1 mg arm, 21% in the 2.5 mg arm, and 4% in the placebo arm. Likewise, grade 3 uric acid increase were observed more frequently in subjects taking EDP-305 with 18% in 1 mg, 19% in 2.5 mg and 4% in placebo. In addition, one subject with a Grade 3 amylase, and one subject with a Grade 3 ALT were reported in the 2.5 mg arm.

There were no clinically significant changes in ECG or vital signs, and no other clinically significant laboratory abnormalities.

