## Final Analysis Statistical Analysis Plan (SAP)

### 9 CHANGES TO PLANNED ANALYSIS FROM STUDY PROTOCOL

This study was terminated by Enanta on October 4th, 2021. At the time the study was terminated no subject had completed Week 72 study assessments. Any analyses planned through week 72 will present all data collected through study termination, and only summary statistics will be provided post Week 12 visit. Any analyses at week 72 will not be performed.

Consequently, the following analyses will not be performed,

SAP Section	Analysis: Endpoint(s)
8.6.2	Primary Efficacy: All
8.2.6.1	Sensitivity Analyses for Primary Endpoints: All
8.6.3.1	Secondary Efficacy Analysis: Categorical Endpoints (Responder at Week 72) – All
8.6.2.3.4	Secondary Efficacy Analysis: Continuous Endpoint Adiponectin through week 72
8.6.4.2	Exploratory Analysis at Week 72: NAFLD Fibrosis Score, AST to Platelet Ratio Index
8.6.4.3	Exploratory Analysis at Week 72: CRP, IL-6, IL-1 $\beta$ , TNF- $\alpha$ , TNF- $\beta$ , alpha2 macroglobulin and haptoglobin levels
8.6.4.5	Exploratory Analysis: ASCVD Score
8.8	Pharmacokinetics (PK) and Pharmacokinetics/Pharmacodynamics (PK/PD) Analysis: All Analyses with the following exceptions: 
 
• Summary of AUC0-8 and AUC2-8 for C4, change from baseline and percentage change from baseline at Week 12 for subjects with and without pruritus
 
• Scatterplot of FGF19 concentrations at Week 12 vs FGF19 Week 12 Change from Baseline value
 
• Scatterplot of C4 concentrations at Week 12 vs C4 Week 12 Change from Baseline value
 
• Scatterplot of Bile Acid concentrations at Week 12 vs Bile Acid Week 12 Change from Baseline value
 
• Boxplot of predose concentration at Weeks 2, 4, 8, and 12 for EDP-305 and EP-022679 by treatment group for subjects with and without pruritus
 
• Listing of EDP-305 & EP-022679 concentrations for subjects with pruritus
 

8.9	Subgroup Analyses: All
8.10.2	Interim Analysis #2: All
8.11	Analysis of COVID-19 Impact on Study: All

- The following listings have been added: Informed Consent and Rescreening data will be listed for all enrolled subjects.
- Inclusion and exclusion criteria will be listed for all enrolled subjects.

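### TEAE percentages are not scaled to time on drug, so adverse events that accrue over time will be understated in any arm that stops treatment earlier

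*SAP*

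**What the plan says.** SAP section 8.7.1 defines a TEAE as "an AE occurring or worsening on or after the first dose of study drug until the last dose of study drug". On the denominator it states "All subjects in the safety analysis set will be included in the summaries", and on the summary measure "All TEAEs will be summarized by SOC, PT and treatment group using frequency counts and percentages". Section 8.5.1 describes duration of exposure by arm, but no adverse event table uses it, and no incidence rate or time-to-event summary is planned. Section 8.7.2 reports subjects meeting the liver stopping rules as counts and percentages.

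Events after the last dose are not dropped: "On-treatment AEs will be summarized separately from those events that occurred during treatment-free follow-up". That second table has its own base: "The denominator for these events will be only those subjects who entered into the 4 week treatment free follow-up period". The lines for SAEs and for AEs leading to death carry no treatment-emergent label.

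The protocol is wider. Section 11.7.2 treats the whole postbaseline phase as treatment-emergent, and the secondary endpoint in section 2.2.2 (repeated in SAP section 4.2) runs through Week 72 and the 4-week follow-up. SAP section 9, written after termination, neither cancels the section 8.7 tables nor lists the narrower TEAE window as a change; for analyses planned through Week 72 it says "Any analyses planned through week 72 will present all data collected through study termination".

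**The concern.** A crude percentage over a window that closes at the last dose gives a subject who stops at Week 6 the same weight as one on drug for a year. If stopping is balanced between arms, this costs little. If it is not, the arm with more early stopping has less time in which later events can be counted, and its percentage falls even when the underlying hazard is the same.

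Unequal stopping is foreseeable here. Protocol section 1.4.2 reports that, over 12 weeks, "the incidence of treatment discontinuation due to pruritus was 1.8% for 1 mg and 20.8% for 2.5 mg and none in the placebo arm". The doses in this trial, 1.5 and 2 mg, lie between those two.

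Frequency of adverse events is a named secondary endpoint. SAP section 9 removes the primary, categorical secondary and subgroup analyses, so safety is among the main between-arm comparisons left. A distortion there that tends to flatter the drug is worth removing if the cost is small.

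**Working it through.** The documents give no adverse event rate, exposure or discontinuation figure for this trial's doses, so there is no planned figure to reproduce. What follows is an illustration.

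**Inputs**
- Share of an EDP-305 arm stopping early, s: 1.8% and 20.8% from Protocol section 1.4.2 (1 mg and 2.5 mg). The 10% value is an assumption; one route to it is given under the objection. Placebo: 0%.
- Assumptions: stops occur at Week 6; all other subjects have T = 24, 36 or 52 weeks on drug; first events follow a constant hazard r of 0.5 or 1 per year, equal in both arms. For rare events, r = 0.05 per year.

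**Formulae**
- Placebo: p(T) = 1 − exp(−rT/52)
- Active: (1 − s)·p(T) + s·p(6)
- Shortfall: s·[p(T) − p(6)]

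**Example** (s = 0.208, T = 36, r = 1): p(36) = 0.4996 and p(6) = 0.1090. Active = 0.792 × 0.4996 + 0.208 × 0.1090 = 0.4183. Identical hazards therefore show as 50.0% on placebo and 41.8% on active, a shortfall of 8.1 points.

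**Shortfall in percentage points**

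| Stopping | T=24, r=0.5 | T=24, r=1 | T=36, r=0.5 | T=36, r=1 | T=52, r=0.5 | T=52, r=1 |
|---|---|---|---|---|---|---|
| 1.8% | 0.3 | 0.5 | 0.4 | 0.7 | 0.6 | 0.9 |
| 10% | 1.5 | 2.6 | 2.4 | 3.9 | 3.4 | 5.2 |
| 20.8% | 3.1 | 5.4 | 4.9 | 8.1 | 7.0 | 10.9 |

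At r = 0.05 the largest value (s = 20.8%, T = 52) is 0.9 points. At T = 36 it is 0.3 points for 10% stopping and 0.6 for 20.8%; the latter is 0.7 of a subject in an arm of 112.

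**Could it hide a real excess?** Multiply the active hazard by 1.2. With no stopping, the crude risk ratio is already only 1.11 to 1.17, because risks compress rates. With 10% stopping it is 1.02 to 1.09; with 20.8% it is 0.92 to 1.00.

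**Does the 4-week follow-up cure it?** Adding 4 weeks to everyone in the example gives p(40) = 0.5366 and p(10) = 0.1749. The shortfall becomes 0.208 × (0.5366 − 0.1749) = 0.075, that is 7.5 points instead of 8.1. A second model (20% risk over 72 weeks, 20.8% stopping spread evenly over Weeks 0 to 12) agrees: 20.0% against 16.2% without the follow-up (ratio 0.81), 21.0% against 17.3% with it (0.82).

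**Does a rate remove it?** Under a constant hazard, expected time at risk to first event is the crude incidence divided by r. In the example that is 0.4996 years per subject on placebo and 0.4183 on active, so the rate is 100 per 100 subject-years in both arms. In the second model it is 16.1 in both.

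**The case against.** The strongest reply is that the premise is unproven. The 20.8% comes from 2.5 mg, which this trial does not use; 1 mg gave 1.8%. Protocol section 4.2.2 expects pruritus in no more than 25% at the chosen doses, against about 51% at 2.5 mg. If the ratio of stops to itch at 2.5 mg carried over (20.8/51, about 0.4; an assumption), 25% itch would mean about 10% stopping, and a true rate ratio of 1.2 would still show above 1. This stands: it bounds the size without removing the mechanism.

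A reader might infer that all adverse event figures for EDP-305 will look falsely low. The documents do not support that. The itch behind the stopping precedes the last dose and is counted in full, and post-dose events have their own table. Termination by the sponsor is administrative and does not by itself favour an arm.

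A reader might also infer that SAEs, deaths and liver stopping-rule events are cut off at the last dose. The SAP does not expressly do that; only related SAEs carry the treatment-emergent label. They are, however, not scaled to observation time, which ends soon after an early stop.

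Finally, safety is descriptive by design and exposure is tabulated by arm, so an imbalance would be visible. That is true, but a reader cannot convert the percentages into rates from those tables.

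**Conclusion.** The point holds in conditional form. If an EDP-305 arm stops drug earlier than placebo, the planned TEAE percentages will understate its later-accruing events relative to placebo. Under the stated assumptions the effect runs from under 1 percentage point at 1.8% stopping, through 1.5 to 5 points at 10%, to 3 to 11 points at 20.8%, and stays under 1 point for rare events. Where between these the trial falls cannot be told from the documents, which give no stopping rate for 1.5 or 2 mg. The claim that a real excess would look like no difference needs stopping close to the 2.5 mg rate and is not established.

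The difference between the SAP's TEAE window and the protocol's does not depend on any of these assumptions and needs reconciling in any case. This is a worthwhile improvement at low cost rather than a defect that invalidates the safety reporting.

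**What to change.** - In SAP sections 8.7.1 and 8.7.2, keep the n (%) tables and add, by arm, subjects with a first event per 100 subject-years at risk. Time at risk runs from first dose to first event, or to the end of the counting window if there is none.
- Give descriptive 95% CIs for rate differences, which is compatible with the SAP's rule of no safety testing. Cover all TEAEs, SAEs, TEAEs leading to discontinuation, preferred terms at 5% or more, and stopping-rule events. State the counting window for SAEs, deaths and stopping-rule events.
- Read late-accruing events from the rates, and early-onset events such as pruritus from n (%).
- Reconcile the SAP's last-dose window with Protocol section 11.7.2 and with the endpoint through Week 72 plus follow-up. Add one combined table through the 4-week follow-up, since two tables with different denominators cannot be added together.

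Cost: SAP wording, some table columns and one table; dose and event dates are already collected. The rate assumes a roughly constant hazard and would overstate early-onset events in a shorter-exposed arm, which is why it should sit beside the percentages and not replace them.
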